# Cue Reactivity Task:

- Inform the participant that we will now run the cue reactivity task
- Receive verbal confirmation that the participant understands the task and the location of the red button
- Inform the participant that he/she will be completing this task five times with a short break in between each run
- Check in with the participant periodically about comfort level

# Example Dialogue:

"Now we will run the cue reactivity task. I want you to press the red button, which is the button furthest from the wire, every time you see an animal that is not a person on the screen. As with the last scan, please stay as still as possible."

# Stroop Task:

- Inform the participants that we will move on to the Stroop task
- Make sure the participant remembers the order of colors on the button box. Explain the order of the buttons to the participants again if need be (closest to the wire is blue, then yellow, then green, then red)
- Explain that first there will be a practice Stroop task. After the practice task inform the participant that they will now begin the real Stroop Task

# Example Dialogue:

"As a reminder, during this task you will be asked to identify the color font of the word you see as quickly and as accurately as you can. The words will be displayed rapidly so do the best you can. We will begin with a practice version and then go into the real task. Do you have any questions?"

# Event-based Reappraisal Task

- Inform the participants that we will move on to the reappraisal task
- The MRI technicians will go in there and switch to the 5-buttons buttonbox
- Explain the instructions one more time
- Ensure that you are using the correct set of images for current participant. After every five participants, we switch to a new set of images. Use same set for each participant's pre/post/

# Example Dialogue:

"In this task, what we are really interested in is people's ability to change how they are feeling. And the way we are going to ask you to change how you are feeling is by changing the way you think about something that we show you. You will see a series of pictures, and some of them are going to make you feel somewhat negative or very negative, and some pictures might not make you feel very negative at all."

# After the Scans:

- Go into the scanner room and help the participant out of the scanner bed. Ask him/her to sit and stand up slowly, as he/she may be dizzy or weak after lying still in the scanner for an extended period of time
- The participant can then change back into street clothes and is free to leave
- Strip the linens off the scanner bed and put them in the hamper along with the participant's used scrubs
- Make a copy of the participant's screening form, give the original to the technician, bring the copy back to CARD, and file in participant's binder

### **Training & Certification**

## Training, Certification, and Supervision of Study Therapists

UP and TC therapists will be experienced clinicians who have undergone training and certification in the treatment protocols utilizing procedures employed in clinical trials at CARD over the last 20 years (e.g., [name] et al., 2000). Training will be done by experts from CARD under the direction of Drs. [name], [name]. Therapists-in-training will attend group supervision meetings, at which both specific application and general issues of these protocols will be discussed. Trainees who have had previous supervised experience with the treatment protocols will not need to complete training cases before starting the certification process.

The certification procedures will consist of systematic review of digital recordings. Using similar procedures and scales to those currently employed across treatment outcome studies at CARD, certification for UP therapists will be completed by expert therapists at CARD and overseen by Drs. [name] and [name]. Initially, expert raters of the protocols will certify the study supervisor (Drs. [name]) who will then be able to certify junior study therapists. All on-going adherence will be conducted by expert raters.

The adherence rating scales are designed to assess three aspects of the therapist's conduct of psychotherapy: adherence to the treatment protocol, skill in administering treatment components, and general therapeutic skill (e.g., attending to signs of disruption of the therapeutic alliance). For initial certification, expert raters listen to all treatment sessions. To be certified, all therapists must receive a score of 85% or higher on at least 20% of the treatment sessions administered. Trainees who do not meet criteria may be given additional training consisting of hour-for-hour supervision of another case and will try for certification again.

#### **Protocol Certification Tracking**

Therapist certification status on the protocols is monitored by the Research Assistant (RA). The RA maintains the Certification and Adherence Tracking Database to track the certification cases each therapist has been assigned to ensure study integrity. The database is organized such that each therapist has their own tab within the Excel spreadsheet that contains all of the certification cases for that therapist.

#### **Training and Certification of IEs**

#### Supervision

After initial training and certification (see Training and Certification Procedures), study therapists are required to meet weekly with a licensed clinician ([name], Project Director) who are trained and certified in the treatment protocols. These supervision meetings are expected to help maintain adherence to the treatment protocols and to help study staff resolve clinical issues that might arise during treatment.

#### **Checks on the Integrity of Assessment Procedures**

The post treatment ADIS and SIGH-A and SIGH-D will be conducted by Independent Evaluators (IEs) who are blind to treatment assignment. It is previously established that double blind procedures are often not completely effective in protecting IEs from accurate guessing of treatment condition (Roll et al., 2004). Based on this knowledge, research personnel will implement all of the steps recommended by Roll et al. (2004) to reduce the occurrence of providing inadvertent clues to treatment assignment and to protect against the impact of possible systematic bias in the responding of IEs.

A large-scale recommendation for reducing systematic bias in the responding IEs includes having a PI and IEs who are affiliated with medical and non-medical professions and incorporating multiple sites in study. A secondary level recommendation requires training to criteria on primary outcome measures and periodic independent monitoring of evaluation implementation and scoring. The third level emphasizes using objective ratings of treatment effectiveness. Other suggestions include keeping the IEs separate from the research team and participants during their treatment sessions and making the participants aware not to reveal too much information to the IE about their treatment sessions and therapists.

The IEs for the proposed study will be Ph.D. or MA-level diagnosticians who have previous research experience with structured interviewing and who will receive additional training and certification for this study under the direction of Drs. [name] and [name]. [name] will supervise the individual training process of the IEs. A two-level system will be used to maintain the reliability of diagnoses and prevent drift in other clinical ratings in the study, consisting of weekly supervision and ongoing rating of selected recordings of clinical assessments. Each month an IE will listen to an assessment performed by another IE associated with the study and independently complete the assessment instruments. These duplicate ratings will be used both to calculate kappa coefficients and for supervision. Differences between raters will be discussed during supervision to identify reasons for disagreement and improve inter-rater reliability. These procedures will help to ensure that IEs refine their diagnostic skills and will also establish common guidelines for ongoing use in diagnostic decision-making. Inter-rater rater reliability (kappa) will be calculated for each of these diagnostic categories: PD/A, SAD, GAD and OCD. Furthermore, IEs will be asked to complete an Independent Knowledge of Treatment form (IEKNO) consistent with previous trials completed at the center, before and after conducting the post ADIS assessment, the one-month follow-up ADIS assessment, and the sixmonth follow-up ADIS assessment.

Copies of this form should also be stored in the Participant Binders in the proper session tabs. After the forms are completed the RA should scan both the pre, and post assessment IEKNO to the StAR 2 shared drive

This form asks the IE to reveal whether the blind has been broken by asking the IE to select the condition which they think the participant has been assigned to and provide any relevant information as to why they believe the participant has been assigned to this condition. The expected rate of guessing correctly will not be greater than chance signifying the maintained blinds. In the event that the IE learns of the condition of the participants, the IE will alert the RA who will schedule future assessment time points with the other IEs who are still blind to the participant's condition. This will only occur when an IE knows for certain which treatment a participant is receiving. If an IE learns that a participant is in treatment (i.e., by seeing them in the waiting area), but does not know which treatment they are in then the IE will not be switched.

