# Consensus

Certified IEs will then meet with the PD each week for ADIS consensus meetings and further supervision on intake procedures. New patients screened for the study will be presented each week to the full research and medical team to inform eligibility for study enrollment following consensus with the PD.

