Session 5	N/A	50 min UP, 30 min TC	30 min	N/A
Session 6	N/A	50 min UP, 30 min TC	30 min	N/A
Session 7	N/A	50 min UP, 30 min TC	30 min	N/A
Session 8	15 min	50 min UP, 30 min TC	30 min	N/A
Session 9	N/A	50 min UP, 30 min TC	30 min	N/A
Session 10	N/A	50 min UP, 30 min TC	30 min	N/A
Session 11	N/A	50 min UP, 30 min TC	30 min	N/A
Session 12 (TC Post)	30 min	30 min TC	1 hour & 15 min	30 min
Session 12 (UP)	15 min	50 min UP	30 min	N/A
Session 13	N/A	50 min UP	30 min	N/A
Session 14	N/A	50 min UP	30 min	N/A
Session 15	N/A	50 min UP	30 min	N/A
Session 16 (UP Post)	30 min	50 min UP	1 hour & 15 min	30 min
1-mo Follow-Up	N/A	N/A	1 hours	30 min
6-mo Follow-Up	N/A	N/A	1 hours	30 min

Scheduling time for each session:

Tracking treatment sessions will be done through Titanium. The therapist should also email the RA the date and time of the next scheduled session as soon as it is scheduled. The RA will check in at weekly lab meetings to make sure the calendar accurately reflects the status of each participant as this information is entered by the RA into Titanium. The RA will schedule time with [name] to complete any necessary procedures.

Note: As of 2020, Titanium is no longer used due to remote procedures. Treatment sessions are now tracked through the "Retention\_ActivePhase" tab of the Retention Database, and a Google calendar

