#### Allowance for Missed/Rescheduled Sessions:

• TC: Participants will receive 12 treatment sessions in 12 to 16 weeks.

• UP: Participants will receive 16 treatment sessions in 16 to 21 weeks.

Participants will have two weeks from the target date to complete each assessment. If a participant fails to contact study personnel for two consecutive weeks, he/she will be withdrawn from the study and informed of study withdrawal via letter sent to his/her home address.

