## Study Gmail Account Login Username and Passwords

## How To Log a Treatment Session in Titanium

- 1. On the calendar screen, right click in the time slot/schedule where you want to add the appointment (Note: By default, weekend days are not displayed but this setting can be changed by your center administrator. To navigate to days not displayed from the calendar screen, click the Go To button on the menu bar and use the calendar pop-up window to select the desired day, or use the arrow navigation icons)
- 2. Click Add > type of appointment to be added and select "Other"
- 3. Enter Appointment Information: Choose an appointment code. In the description write StAR2, participants ID number, and session number. Also be sure to mention the RA and type of visit (health/med or ADIS).

(Note: Do not put confidential information in these fields.)

- 4. Click the Scheduling tab to add the **room number** so the appointment is added to this schedule
- 5. Click Save (Note: Depending on the settings chosen by your center administrator, you may see prompts to add the appointment to your schedule, that either you or the client has a conflicting appointment, or assign a new client to yourself).
- 6. After making the appointment for the participant, make sure to add it to the calendar of the person overseeing the visit:
  - a. If **RA** portion, add the appointment to the RA's calendar.
  - b. If ADIS screening or post-assessment add appointment to the IE's calendar.
  - c. If **health/med** portion add appointment to [name]'s calendar and schedule a medical room under the "Scheduling" tab.
  - d. If therapy appointment, add to the therapist's calendar.
- 7. Click Exit.

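### The evaluators' post-treatment visit falls at session 12 in TC and session 16 in UP, and nothing in the plan masks session number or visit timing from evaluators it calls blind

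*Combined protocol and SAP*

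**What the plan says.** **The blind.** Checks on the Integrity of Assessment Procedures states that "The post treatment ADIS and SIGH-A and SIGH-D will be conducted by Independent Evaluators (IEs) who are blind to treatment assignment". It concedes that such blinds often leak and undertakes to reduce inadvertent clues. IEs record a guess of the arm before and after the post-treatment, 1-month and 6-month interviews. Correct guesses are expected not to exceed chance, but no rate is given. An IE is replaced only when certain of the arm, and the replacement covers future time points.

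**The visit.** The session table in Scheduling/Tracking Sessions books IE time at the rows "Session 12 (TC Post") and "Session 16 (UP Post"). The assessment schedule likewise places the last-session battery at 12 or 16.

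**The calendar.** How To Log a Treatment Session in Titanium instructs: "In the description write StAR2, participants ID number, and session number". The same step asks for the visit type and names ADIS visits as an example. A later step reads: "If ADIS screening or post-assessment add appointment to the IE's calendar". Scheduling/Tracking Sessions notes that "As of 2020, Titanium is no longer used due to remote procedures" and names a Retention Database tab and a Google calendar as replacements, without saying how entries are labelled or who sees them.

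**The timing.** Under Allowance for Missed/Rescheduled Sessions, TC runs 12 to 16 weeks, and "UP: Participants will receive 16 treatment sessions in 16 to 21 weeks". Randomization allows up to 4 weeks between the baseline assessment and session 1. IEs conduct the intake interview, and under Consensus, "New patients screened for the study will be presented each week to the full research and medical team".

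**The concern.** The two arms have different numbers of sessions, and the IE's visit is tied to the last one. Anything that shows an IE the session number, or how long the participant has been in the study, is therefore a clue to the arm. The written calendar rule supplied the first clue directly. The IE's own part in intake supplies much of the second.

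At stake are the ratings that the blind exists to protect. SIGH-A and SIGH-D are two of the four anxiety and depression measures in Aim 3. The ADIS severity ratings and the IE's CGI are made on the same occasion. If IEs know or strongly suspect the arm, part of any UP advantage on these measures could be rater expectation, and the trial could not separate the two.

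The replacement rule does not repair this. It acts on later visits, so the post-treatment rating has already been made. A strong but uncertain inference does not trigger it at all.

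**Working it through.** The plan gives no guess rate or chance level, so there is no figure of its own to reproduce.

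**Step 1: session number.** The post visit is at session 12 in TC and 16 in UP. An entry labelled 12 or 16 and marked as a post-assessment identifies the arm for any participant on schedule.

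**Step 2: how many visits the Titanium rule could reach.** Recruitment began in August 2017 (Study Timeline). Table 1 projects 5 + 15 = 20 of 60 randomized in Years 1 and 2, before Titanium was dropped. This is a projection, not an accrual count.

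**Step 3: chance under 40:20.** Always guessing UP is right 40/60 = 66.7% of the time. Guessing in proportion gives (2/3)² + (1/3)² = 55.6%. A coin gives 50%.

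**Step 4: elapsed time from screening.**
- Inputs: TC 12–16 weeks, UP 16–21 weeks, lag from screening to session 1 of 0–4 weeks.
- Assumption: all three are uniform and independent. The plan gives only the limits.
- Ranges: TC 12–20 weeks and UP 16–25 weeks, overlapping in weeks 16–20.
- Share in the overlap: half of TC, by symmetry about week 16; and 4²/(2 × 5 × 4) = 16/40 = 40% of UP.

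For a cut at c weeks within the overlap:
- TC correct = 1 − (20 − c)²/(2 × 4 × 4) = 1 − (20 − c)²/32
- UP correct = 1 − (c − 16)²/(2 × 5 × 4) = 1 − (c − 16)²/40

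| Cut (weeks) | TC correct | UP correct | Overall |
|---|---|---|---|
| 18.25 | 1 − 3.0625/32 = 90.4% | 1 − 5.0625/40 = 87.3% | 88.9% (arms weighted equally) |
| 17.54 (best under 2:1) | 1 − 6.059/32 = 81.1% | 1 − 2.367/40 = 94.1% | (81.1 + 2 × 94.1)/3 = 89.7% |

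The 2:1 cut solves (1/3)(20 − c)/16 = (2/3)(c − 16)/20, so c = 912/52 = 17.54.

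**Step 5: sensitivity to shape.** These are simulated best guesses under 2:1, with beta-distributed timing inside each window and a uniform 0–4 week lag unless stated.

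| Timing inside the windows | Correct |
|---|---|
| Uniform, lag 1–4 weeks | 92% |
| Both arms early, beta(1,3) | 94% |
| Both arms late, beta(3,1) | 95% |
| Both arms central, beta(2,2) | 93% |
| TC late, UP early (least favourable to guessing) | 79% |

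**Step 6: elapsed time from session 1.** The windows 12–16 and 16–21 meet only at week 16. However, the plan allows two weeks from the target date for each assessment. If that applies to the post visit, the ranges become 12–18 and 16–23 weeks. With a uniform 0–2 week delay, the best cut is right about 94% of the time with the arms weighted equally. The same delay brings the figure from screening to about 88%.

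**Step 7: what the guess data could show.** Let X be the number of correct guesses among 60, if all 60 have one.
- Against 2/3: P(X ≥ 46) = 0.063 and P(X ≥ 47) = 0.034, so 47 correct would exceed chance at one-sided 5%.
- Against 1/2: P(X ≥ 37) = 0.046. An evaluator who always says UP scores 40, and would appear unblinded while knowing only the allocation ratio.

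**The case against.** **The calendar rule is retired.** This stands for current practice. Titanium was dropped in 2020, and silence about the Google calendar does not show that session numbers appear there. But the instruction remains in the manual without a retirement note of its own, the earlier visits were made under it, and its successor has no masking rule.

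**The post-assessment entry may not have carried a 12 or 16.** The instructions are headed as logging a treatment session, so this is an inference. It is a reasonable one: the step that requires the session number names ADIS visits, and a later step sends the post-assessment to the IE's calendar.

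**Duration alone reveals the arm.** A reader might infer this from the non-overlapping treatment windows. The documents do not support it. Nothing shows that IEs learn the session 1 date. From screening, weeks 16–20 are shared. Participants who drop out or are withdrawn can have post-treatment assessments off schedule (Premature Study Termination; When to Withdraw Participants from the Study; Drop-Outs), which blurs timing further. It also means that not every case is identified by a session number.

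**The ratings are effectively open-label.** This too goes further than the evidence. Timing moves the best guess from 67% to about 90%, which is a serious leak but not certainty.

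**Safeguards exist.** The IE alert in Assessment Tracking and Scheduling lists only initials, date and time. The knowledge-of-treatment form already asks what led to the guess. An IE who becomes certain must say so and is replaced at later visits. All this is correct, and it makes changes to the alert or an extra form item largely redundant. None of it masks the calendar or protects the post-treatment rating.

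**Conclusion.** The concern holds in a limited form. The plan states a blind for the IE-rated outcomes, ties the IE's post visit to an arm-specific session, and does not mask session number or timing. Under the Titanium rule, the session number revealed the arm for participants on schedule, provided that the post-assessment entry was labelled as the instructions direct. For later visits, what IEs could see is not documented.

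Elapsed time from screening supports a correct guess about 90% of the time (79% to 95% across the shapes tried), against 67% from always guessing UP. These figures rest on assumed distributions inside the stated windows, and on an IE who knows the screening date and both treatment lengths.

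The scope is the ADIS, SIGH-A, SIGH-D and the IE's CGI at post-treatment, with any carry-over to follow-up. It would be wrong to extend the point to the primary outcome. Drinks per week comes from the Timeline Follow-Back, which research assistants administer outside the IE blind. OASIS and ODSIS are self-reported. The documents do not show that ratings were in fact biased, only that a route for bias was left open.

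**What to change.** 1. **Neutral labels.** Amend How To Log a Treatment Session in Titanium, and the current Google calendar and Qualtrics practice. Every IE visit after randomization should be entered as an IE assessment with ID, date and time only. IEs should not be able to see the treatment-session calendar or session-numbered survey folders.
2. **A different rater after intake.** Where an existing blind IE is available, assign the post-treatment and follow-up ratings to one who did not do that participant's intake. The plan already presumes that other blind IEs exist.
3. **A stated benchmark.** Compare the recorded guesses with 67% (always guessing UP under 2:1) in place of an unspecified chance level. Report the IE-rated outcomes alongside that accuracy, including for visits already completed. The guess made before the post-treatment interview is the most useful, because it reflects what was known or inferred before that interview began.

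The cost is rewording, relabelling and access settings, plus some loss of rater continuity between intake and post-treatment. No new staff or assessments are needed. If few visits remain, item 3 still applies in full because the guesses are already being collected.

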# Table 1. Visit Projection Table

#### **Subjects**

A total of 60 participants will be enrolled, with a target male to female ratio of 33:27. This ratio reflects the higher prevalence rates of AUDs in biological men compared to biological women. Forty participants will be randomized to the UP condition and 20 to the Take Control condition. In addition, 25 participants from the UP group will receive two fMRI scans (pre- and post-treatment).

Participants will be recruited via flyers, brochures, lab website and StAR Facebook page, MBTA advertisements, etc. Telephone screenings will determine initial eligibility, and potential research participants will be invited to CARD, located at Boston University, for a more extensive assessment of alcohol use and emotional disorders.

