#### Randomization

Prior to the start of the trial, a random number generator was used to establish a randomization schedule that assigns participants to either the active treatment (UP) or comparison condition (TC). Once a new participant is enrolled in the trial, the RA will refer to the next assignment in the randomization schedule

The current trial aims to recruit 40 participants in the UP condition and 20 participants in the TC condition.

Once the participant is randomized, the RA will contact the participant to discuss scheduling and provide further information about length of the trial. TC participants will complete 12 sessions of therapy (in a maximum of 16 weeks), while UP participants will complete 16 weeks of therapy (in a maximum of 21 weeks). Additionally, follow-up assessments will be completed at one month and six months posttreatment.

If the participant is randomized to TC, the next session is session 1, and the RA will schedule the session based on the participant's and assigned therapist's availability. If the participant is randomized to the UP condition, the RA will potentially schedule the participant

for the fMRI session prior to scheduling session 1 with the therapist. The first study session will be scheduled within 4-weeks after the in-clinic baseline assessment. If the one-month window expires before the participant can complete the first session, then the assessment must be repeated to assess the participant's continued eligibility for the study (a "refresher").

To schedule an fMRI session, the RAs will need to refer to the CILSE scheduling calendar to confirm that the scanner and the MRI technicians are available and to book the appointment. The RA will need to book 30 minutes in the

Med Lab at CARD for the urine, drug, and/or pregnancy test, and 1.5 hours at CILSE for the scan. Once appointments are scheduled, the RA will document the time and date for all involved study staff in Titanium (see How to Log a Treatment Session in Titanium).

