# **Measures of Study Integrity**

Treatment Involvement Form (TIF; adapted from ACAP and LTS study forms): The TIF-TTS edition is a 7-item questionnaire that asks about any changes in medication, treatment, or lifestyle since the last assessment time point. At the beginning of each assessment, with the exception of the Screening Session, the RA administers the TIF to the participant and reviews it after every session. Any changes should be reported to the attending clinician. TIF is designed to assess for whether the participant has sought treatment/services outside of their study therapy sessions. It is used to determine start of treatment and/or change in treatment.

Knowledge of Treatment Form (KNO; as used in Roll et al., 2004): The IEs complete the KNO form before and after the post, 1-month, and 6-month ADIS assessment. The main functionality of the KNO is to determine whether the blind has been broken during the post assessment, or any other time leading up to the assessment. Roll et al. (2004) suggest that study integrity should try to be maintained by having evaluators who are blind to treatment condition to prevent any biases. The current version of the KNO is a 3-item questionnaire that asks the evaluator to guess which condition they believe the participants is in and how confident they are that the participant is in

that condition on a 0 to 8 Likert scale (0=Not at all, 4=Somewhat, 8=Absolutely). The last item asks the evaluator to disclose any information that may have contributed to a potential blind break.

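### The evaluator blinding check compares correct guesses with an undefined chance rate, and under 40:20 allocation no single rate can serve as that benchmark

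*Combined protocol and SAP*

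**What the plan says.** Allocation is 2:1. The Subjects section states: "Forty participants will be randomized to the UP condition and 20 to the Take Control condition". The Randomization section repeats it: "The current trial aims to recruit 40 participants in the UP condition and 20 participants in the TC condition".

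Under Checks on the Integrity of Assessment Procedures, the blind is examined with a form "asking the IE to select the condition which they think the participant has been assigned to". The inference to be drawn is: "The expected rate of guessing correctly will not be greater than chance signifying the maintained blinds". That section gives no value for chance, no test, no significance level and no breakdown by arm.

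Measures of Study Integrity describes the form as three items: the guess, a 0-8 confidence rating, and a disclosure item ("The last item asks the evaluator to disclose any information that may have contributed to a potential blind break"). On timing it says: "The IEs complete the KNO form before and after the post, 1-month, and 6-month ADIS assessment". It describes no analysis of any of the three items.

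**The concern.** Percentage correct mixes two things: whether the evaluator can tell the arms apart, and how often the evaluator happens to guess the larger arm. With equal allocation the second cancels, and 50% is the uninformed rate whatever the guessing habit. With 40:20 it does not cancel, so comparison with one chance rate cannot separate information from habit.

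The conclusion at stake is that the ADIS, SIGH-A, SIGH-D and evaluator CGI ratings were made blind. Aim 3 compares the arms on SIGH-A and SIGH-D. The two treatments also differ in length (12 sessions against 16), so cues to arm are plausible. Evaluators are reassigned only when they are certain of the arm, so partial unblinding would be seen only through the guess data.

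**Working it through.** The plan states no figure for chance, so there is none to reproduce.

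**Inputs.** 40 UP, 20 TC, 60 in total (Subjects; Randomization). Assumed, because the documents are silent: chance is either 50% or 2/3; exact binomial test at 0.05; all 60 assessed; guesses independent.

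**Step 1: expected rate with no information.** If UP is guessed with probability g regardless of arm, the expected proportion correct is (2/3)g + (1/3)(1 − g).

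- Coin flip, g = 1/2: 50.0%.
- Ratio-matched, g = 2/3: 4/9 + 1/9 = 55.6%.
- Always UP, g = 1: 40/60 = 66.7%.
- Always TC, g = 0: 20/60 = 33.3%.

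**Step 2: chance read as 50%.** The one-sided cut-off is 37/60 (two-sided 39/60). Always UP gives 40/60: P(X ≥ 40) = 0.0067 one-sided, 0.0135 two-sided. For other values of g, the number correct is Binomial(40, g) + Binomial(20, 1 − g), and the chance that an uninformed evaluator reaches 37/60 is:

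| g | Expected correct | Flagged (one-sided 0.05) |
|---|---|---|
| 0.5 | 50.0% | 4.6% |
| 2/3 | 55.6% | 19% |
| 0.8 | 60.0% | 44% |
| 0.9 | 63.3% | 75% |
| 1.0 | 66.7% | 100% |

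With fewer assessed and the ratio kept, always UP gives one-sided p = 0.015 at 32/48, 0.022 at 28/42 and 0.049 at 20/30. The last is 0.099 two-sided.

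**Step 3: chance read as 2/3.** The always-UP evaluator now passes: P(X ≥ 40) = 0.56. But suppose evaluators identify all 20 TC participants and flip a coin for UP, with 20/40 correct. The total is again 40/60, with the same p = 0.56. Yet TC is guessed for 20/20 TC participants and 20/40 UP participants (Fisher two-sided p about 0.000035). The one-sided cut-off against 2/3 is 47/60, so these evaluators would be flagged only if at least 27 of the 40 UP guesses were right: P(Binomial(40, 0.5) ≥ 27) = 0.02.

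**Step 4: measures that separate the cases.** Bang's index in an arm, with a forced guess, is 2 × (proportion correct) − 1. Kappa is (observed − expected agreement)/(1 − expected agreement).

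| Pattern, 40/60 correct in both | Bang UP | Bang TC | Kappa |
|---|---|---|---|
| Always UP, no information | +1 | −1 | (0.667 − 0.667)/(1 − 0.667) = 0 |
| All TC identified, coin flip in UP | 0 | +1 | (0.667 − 0.444)/(1 − 0.444) = 0.40 |

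In the second row, TC is guessed 40/60 times, so expected agreement is (2/3)(1/3) + (1/3)(2/3) = 0.444. The overall percentage is identical in the two rows; the arm-specific and chance-corrected measures are not.

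**Step 5: precision.** With random guessing, the 95% half-width of Bang's index is 1.96 × 2 × √(0.25/n): 0.44 for n = 20 and 0.31 for n = 40.

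**The case against.** The sentence is worded as an expectation. No test or threshold is attached, and the one operational rule, replacing an evaluator who is certain of the arm, does not use the guess rate. Nor does the text forbid reporting by arm. This is fair, and it means that no formal decision rule is being broken. But the sentence does say what a rate no greater than chance would signify, and nothing elsewhere in the document replaces that inference. Premature Study Termination refers to a data analysis section of the grant, which is not in this document; more detail may sit there.

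A reader might infer that an evaluator who always guesses UP will look unblinded. The documents do not support that, because it follows only if chance means 50%, a figure they never give. Against 2/3, or with kappa, that evaluator passes.

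The worst case is also extreme. It needs every guess to be UP although several evaluators rate, all 60 assessed at 2:1, and independent guesses although they cluster within a few evaluators. No section says evaluators know the ratio, and the randomization list is limited to research assistants and the investigator. A lean to UP does not require that knowledge, however.

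Nor should one infer that unblinding in one arm escapes under either reading. At 50%, complete unblinding of one arm with coin-flip guesses in the other gives an expected 40/60 (TC) or 50/60 (UP), both above the cut-offs. The missed case in step 3 belongs to the 2/3 reading.

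**Conclusion.** The point stands as a gap in definition with practical consequences. Neither obvious fixed rate works: 50% turns a guessing habit into apparent unblinding, and 2/3 lets complete identification of the TC arm through. The same 40/60 gives p = 0.007 or p = 0.56 depending on an unstated null, and neither answer says whether the arms were told apart. The sizes assume N = 60 at 2:1, a 0.05 level and independent guesses; unequal dropout would shift them. The patterns are illustrations, not predictions of how these evaluators will guess.

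A reader might extend this to the main efficacy result, but the documents do not support that. The primary outcome is drinking from the TLFB, now taken by a research assistant, and OASIS and ODSIS are self-reported. This is a minor, worthwhile correction.

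**What to change.** Replace the overall-rate criterion. For the pre-interview and post-interview forms at each of the three assessments, tabulate guess by actual arm and report Bang's index in UP and in TC with 95% CIs, reading the two together: +1 in UP with −1 in TC is a habit of guessing UP, not unblinding. At minimum, compare the proportion guessing UP between the arms. Treat the 0-8 confidence rating as descriptive unless a weighting is specified in advance.

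The guesses are already collected, so the cost is a short addition to the analysis plan. The full version yields 2 arms × 2 forms × 3 assessments = 12 indices. Those for TC will be imprecise, so a TC interval that includes zero should not be taken as proof that the blind held.
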